7.1.2 Demographics

Demographic information (date of birth, gender, race, ethnicity) will be recorded at Screening.

7.1.3 Medical History

Relevant medical history, including history of current disease, other pertinent respiratory history (e.g., tobacco use), and information regarding underlying diseases will be recorded at Screening and a focused medical history on symptoms/toxicity will be performed thereafter.

7.1.4 Physical Examination

A complete physical examination including height (at screening only), weight, ECOG performance status and vital signs (temperature, pulse, blood pressure) will be performed by either the investigator or a sub-investigator. New abnormal physical exam findings must be documented and will be followed by a physician or other qualified staff (MD, NP, RN, and PA) at the next scheduled visit.

7.1.5 Adverse Events

Events should be assessed per NCI-CTCAE criteria v5.0. Information regarding occurrence of adverse events will be captured throughout the study. Duration (start and stop dates), severity/grade, outcome, treatment and relation to study drug will be recorded in the electronic case report form (eCRF).

7.1.6 Disease Assessment

Baseline disease assessment should be obtained within 4 weeks prior to treatment initiation. Assessment of disease will then occur during follow-up, every 6 months for 3 years.

7.2 Clinical Laboratory Assessments

7.2.1 Hematology

Blood will be obtained and sent to the clinical site laboratory for a complete blood count with white blood cell differential.

7.2.2 Blood Chemistry Profile

Blood will be obtained and sent to the clinical site laboratory for determination of comprehensive metabolic panel (sodium, potassium, chloride, CO₂, BUN, creatinine, glucose, calcium, albumin, total protein, total bilirubin, AST, ALT, alkaline phosphatase), magnesium and phosphorus.

7.2.3 Thyroid panel

Blood will be obtained and sent to the clinical site laboratory for determination of thyroid-stimulating hormone (TSH). Free T₄ and free or total T₃ will only be measured if TSH is abnormal or if there is a clinical suspicion of an AE related to the endocrine system.

7.2.4 PT/INR

Blood will be obtained and sent to the clinical site laboratory for determination of PT/INR at screening and pre-surgery.

7.2.5 Pregnancy Test

A serum pregnancy test will be obtained from female subjects who are of childbearing potential prior to their participation in the study and prior to each subsequent dose of pembrolizumab.

7.3 Correlative Studies Procedures

7.3.1 Archival Tumor Tissue

Archived primary tumor in fixed paraffin-embedded blocks or slides from the diagnostic TURBT specimen of each subject must be requested at baseline for correlative studies. Additionally, we will request banked tissue on the subset of patients who have previously had tissue frozen via UNC's Tissue Procurement Facility's standing collection protocol, or through our group's biospecimen repository protocol (LCCC1212).

mRNA Sequencing and Gene Expression Profiling

RNA will be extracted from tumor samples, libraries will be prepared using the TruSeq RNA Access protocol. mRNA libraries will be sequenced, and relevant gene expression signatures will be evaluated, including relative expression of preand post-treatment STAT3 and NF- κ B signatures, IFN γ -related genes, MHC class I/II genes, and immune checkpoint genes and other immune gene signatures.

Immunohistochemistry

Histone acetylation (H3K9Ac and H3K27Ac) levels will be assessed via immunohistochemistry.

Whole Exome Sequencing

DNA will be extracted and whole-exome sequencing libraries will be generated. Exome sequence data will be processed using the established pipeline developed at UNC. Buccal swabs will be used as a source for normal DNA.

ChIP-Sequencing

For the subset of patients with frozen diagnostic TURBT and post-treatment surgical tissue available, we will perform ChIP-sequencing for H3K27Ac and other histone markers (H3K4Me3 and K3K27Me3, etc.) to assess where changes in histone post-translational modifications associate with active transcription.

T Cell Receptor Repertoire Profiling: immunoSEQ Assay
TCR repertoire amplification and sequencing will be done on tumor and
peripheral blood samples after DNA extraction. The TCRb CDR3 regions will be
amplified and sequenced using immunoSEQ. Pre- and post-treatment TCR
repertoire clonality will be compared to assess for an antigen-specific immune
response.

7.3.2 Blood samples

Subjects will have their blood collected in ACD tubes (whole blood) at Day 1, Day 8, and Day 22 of study treatment, and at the time of post-treatment surgery (cystectomy or maximal TURBT). Sample collection and storage instructions for peripheral blood mononuclear cells and plasma samples is provided in the Laboratory Manual.

7.3.3 Tumor and Lymph Node Tissue from Post-Treatment Surgery (Cystectomy or maximal TURBT)

Tumor tissue will be flash frozen and FFPE tissue will be collected for analysis to ensure comparability of samples between diagnostic TURBT and post-treatment surgery (cystectomy or maximal TURBT). Next generation sequencing and IHC studies will be done on post-treatment surgical tumor samples as above in Section 7.3.1 for diagnostic TURBT samples. Remaining tissue may be stored for future research with subject's permission through our biospecimen repository protocol (LCCC1212), or, if requested, any unused slides will be returned to the site of origin. Otherwise, all remaining tissue will be destroyed per institutional guidelines. Additional details of correlative studies are provided in the accompanying Laboratory Manual.

7.3.4 Urine Microbiome

Urine for microbiome analysis will be collected by either clean catch and/or catheterization. The catheterization collection method will only be used to collect urine in cases where the subject will be undergoing bladder catheterization as part of routine care. Urine will be frozen and stored until time of sequencing. 16S ribosomal sequencing is currently planned to be carried out in conjunction with the UNC microbiome core (https://www.med.unc.edu/microbiome/).

8.0 EVALUATIONS AND ASSESSMENTS

8.1 Time and Events Table

Assessments	Screening ²		Trea	tmen	t ¹	Pre-		Post-	Follow-
Assessments	Screening	D1	D8	D15	D22	Surgery ¹²	Surgery ¹	Surgery ¹³	up ¹⁴
Informed consent	×								
History	×	×			×	×12		×	
Physical exam	×	×			×				
Performance status	×	×							
Tumor imaging ³	×								×
Pregnancy test ⁴	×				×				
Hematology ⁵	×	×	×	×	×	×			
Serum chemistries ⁶	×	×	×	×	×	×			
Thyroid panel ⁷	×					×			
PT/INR	×					×			
Toxicity assessment	×	×	×	×	×	×12		×	
Concomitant medications	×	×	×	×	×	× ¹²	×		
Pembrolizumab IV		×			×				
Entinostat PO ⁸		×	×	×					
Archival tissue collection ⁹	×								
Blood sample for correlatives ¹⁰		×	×		×		×15		
Fresh tissue collection							×		
Urine collection	×					×			
Buccal swab ¹¹	×								
Survival									×

Footnotes to Time and Events Table

- 1. A window of ±1 day will be applied to study visits on Day 1, Day 8, Day 15 and Day 22. Post-treatment surgery refers to radical cystectomy or maximal TURBT and should occur within 10 weeks from the time of initiation of study therapy.
- 2. Unless otherwise noted, laboratory evaluations may be performed up to 10 days prior to first dose of the clinical trial treatment. Laboratory assessments on day 1 do not need to be repeated if screening labs were performed less than 72 hours prior to the scheduled visit.
- 3. Tumor imaging should include MRI scan or contrasted CT of abdomen and pelvis and CT scan of the chest within 4 weeks prior to treatment initiation and during follow up..
- 4. Serum βhCG must be performed within 72 hours prior to pembrolizumab administration for women of childbearing potential.
- 5. Hematology must include complete blood count with white blood cell differential.
- 6. Serum chemistry must include: sodium, potassium, chloride, CO₂, BUN, creatinine, glucose, calcium, albumin, total protein, total bilirubin, AST, ALT, alkaline phosphatase, magnesium, phosphorus.
- 7. Free T₄ and free or total T₃ will only be measured if TSH is abnormal or if there is a clinical suspicion of an AE related to the endocrine system.
- 8. In Arm 2 only. Entinostat should be taken before the pembrolizumab infusion.
- 9. Fixed paraffin-embedded blocks or slides from the diagnostic TURBT specimen must be requested for subjects at baseline. Sample collection, storage, and shipment instructions for tumor tissue samples are provided in the Laboratory Manual.
- 10. Blood sample to be obtained in ACD tubes for correlative studies prior to first dose of the study treatment on Day 1 and Day 22 prior to administration of pembrolizumab, and at the time of post-treatment surgery. Sample collection, storage, and shipment instructions for serum samples will be provided in the Laboratory Manual.
- 11. Buccal swabs will be collected for correlative assays at screening. May be repeated if amount collected at baseline is not sufficient for analysis.
- 12. Visit will be scheduled as per standard of care. Collection of history, toxicity assessment, and concomitant medications at the pre-surgery visit is only required for subjects receiving a cystectomy (i.e. not those receiving bladder preserving maximal TURBT). Samples for safety labs (hematology, serum chemistries, thyroid panel, and PT/INR) are required for all subjects and may be collected at the same time as blood samples for correlatives, up to 2 days before surgery.
- 13. The post-surgery visit should be scheduled 2-4 weeks after maximal TURBT (for trimodality subjects) and 4-8 weeks after cystectomy for cystectomy patients. Serious adverse events (SAEs) caused by a protocol-mandated intervention, or any grade of events of clinical interest (see section 9.4.2.2) that occur within 90 days of the last pembrolizumab administration must be recorded. Collection of potential serious adverse events and/or events of clinical interest will occur during regular follow-up visits scheduled per community standards of medical care.
- 14. Subjects will be followed every 6 months for 3 years after surgery for recurrence and survival. Survival status maybe obtained by remote means.
- 15. A window of –2 days will be applied to correlative samples collected at the surgery visit. This should not occur after surgery.

CONFIDENTIAL UNIVERSITY OF NORTH CAROLINA January 9, 2025

LCCC 1827 PI: [name], MPH Amendment 6

8.2 Post-Treatment Surgery

Post-treatment surgery (either cystectomy or maximal TURBT for trimodality patients) should occur within 10 weeks of the initiation of study therapy. For cystectomy subjects, the surgery with curative intent will occur as per routine clinical standard of care and will be performed at the discretion of the surgeon. For subjects undergoing trimodality therapy, maximal TURBT should occur within 10 weeks of initiation of study therapy, followed by initiation of standard of care concurrent chemotherapy and radiation.

Tissue acquisition: A sample of tumor tissue from the post-treatment surgery will be preserved for correlative studies. A sample of lymph node tissue from the lymph node dissection, if available, and normal tissue from the cystectomy specimen will be preserved for correlative studies from all cystectomy subjects. These tissues will be preserved in consultation with surgical pathology, and tissue released for correlative studies post pathological review. Note: Subjects who do not complete clinical trial treatment for whatever reason other than withdrawal from the study, but still undergo surgery, will be requested to participate in correlative studies.

Blood sample for correlative studies: blood will be collected in ACD tubes (see Study Laboratory Manual for details).

8.2.1 Post-Surgery Visit

This visit should be scheduled 4-8 weeks after cystectomy, or 2-4 weeks after maximal TURBT for trimodality subjects. This visit should occur prior to initiation of subsequent standard of care chemotherapy and radiation in trimodality subjects. Initiation of chemotherapy and radiation should occur per standard of care after maximal TURBT. Serious adverse events (SAEs) related to protocol-mandated treatment or any grade of Events of Clinical Interest (see section 9.4.2.2) that occur within 90 days of pembrolizumab administration must be recorded.

8.3 Handling of Biospecimens Collected for Correlative Research

Biospecimens collected for this study will be stored in the Lineberger Comprehensive Cancer Center (LCCC) Tissue Procurement Facility (TPF), or if needed, in a secure off-site storage facility. All biospecimen samples will be obtained in accordance with procedures outlined in the LCCC 1827 Study Laboratory Manual and stored in containers with controlled access. Each sample will be assigned a unique code number and no identifiable personal health information (PHI) will be on the specimen label. Information about the subject's disease will be linked to the specimens stored in the repository database. TPF-associated research staff, LCCC Bioinformatics staff who support the TPF database and the LCCC Data Warehouse, and researchers with IRB-approval for access to PHI for each subject in this study will be able to link specimens to

relevant medical information. Some results from laboratory analyses that occurred during the subject's participation in the clinical study may also be included.

Storage Time:

- The biospecimen will be used first and foremost for research purposes outlined within the confines of this protocol. Samples will be discarded/destroyed after relevant data are collected for this study; unless consent was obtained from the subject to use tissue for other research purposes (Specimen Consent checkbox was checked, and consent was signed).
- Leftover biospecimen material collected during this study may be stored and used for other research purposes including genetic research only if subject's assent was obtained. In this circumstance, there is a 15-year limit on use and storage of the biospecimens. If storage is anticipated to be indefinite, there will be an opt-out on the informed consent form allowing subjects to choose not to allow their specimens to be used for such future research.

Compliance Statement

Biospecimen collection for this study will be conducted in full accordance to all applicable University of North Carolina (UNC) Research Policies and Procedures and all applicable Federal and state laws and regulations including 45 CFR 46, and the Health Insurance Portability and Accountability Act (HIPAA) Privacy Rule. Any episode of noncompliance will be documented.

The investigators will perform the study in accordance with this protocol, will obtain consent and assent (unless a waiver is granted), and will report unexpected problems in accordance with The UNC IRB Policies and Procedures and all federal requirements. Collection, recording, and reporting of data will be accurate and will ensure the privacy, health, and welfare of research subjects during and after the study.

8.4 Assessment of Safety

Any subject who receives at least one dose of study therapy on this protocol will be evaluable for toxicity. Each subject will be assessed periodically for the development of any toxicity according to the Time and Events table. Toxicity will be assessed according to the NCI CTCAE version 5.0.

9.0 ADVERSE EVENTS

9.1 Definitions

9.1.1 Adverse Event (AE)

An adverse event (AE) is any untoward medical occurrence (e.g., an abnormal laboratory finding, symptom, or disease temporally associated with the use of a drug) in a subject or clinical investigation subject administered a pharmaceutical product and which does not necessarily have a causal relationship with this treatment. An AE can therefore be any unfavorable and unintended sign (including an abnormal laboratory finding), symptom, or disease temporally associated with the use of a medicinal product, whether or not related to the medicinal product.

Hospitalization for elective surgery or routine clinical procedures that are not the result of an AE (e.g., surgical insertion of central line) need not be considered AEs and should not be recorded as an AE. Disease progression should not be recorded as an AE, unless it is attributable by the investigator to the study therapy. Adverse events may occur during the course of the use of Merck product in clinical trials, or as prescribed in clinical practice, from overdose (whether accidental or intentional), from abuse and from withdrawal.

All AEs, SAEs and other reportable safety events that occur after the consent form is signed but before treatment assignment must be reported by the investigator if the event causes the subject to be excluded from the study or is the result of a protocol-specified intervention, including but not limited to washout or discontinuation of usual therapy, diet, or a procedure.

- All AEs from the time of treatment through 30 days following cessation of study therapy must be reported by the investigator.
- All AEs meeting serious criteria, from the time of treatment through 90 days following cessation of study treatment, or 30 days following cessation of study treatment if the participant initiates new anticancer therapy, whichever is earlier must be reported by the investigator.
- All pregnancies and exposure during breastfeeding, from the time of treatment through 120 days following cessation of study treatment, or 30 days following cessation of study treatment if the participant initiates new anticancer therapy must be reported by the investigator.
- Additionally, any SAE brought to the attention of an investigator at any time outside of the time period specified above must be reported immediately by the investigator if the event is considered to be drugrelated.

Investigators are not obligated to actively seek AE or SAE or other reportable safety events in former study participants. However, if the investigator learns of any SAE, including a death, at any time after a participant has been discharged from the study, and he/she considers the event to be reasonably related to the study treatment or study participation, the investigator must promptly notify Merck.

9.1.2 Suspected Adverse Reaction (SAR)

A suspected adverse reaction (SAR) is any AE for which there is a *reasonable possibility* that the drug is the cause. *Reasonable possibility* means that there is evidence to suggest a causal relationship between the drug and the AE. A suspected adverse reaction implies a lesser degree of certainty about causality than adverse reaction, which means any adverse event caused by a drug.

Causality assessment to a study drug is a medical judgment made in consideration of the following factors: temporal relationship of the AE to study drug exposure, known mechanism of action or side effect profile of study treatment, other recent or concomitant drug exposures, normal clinical course of the disease under investigation, and any other underlying or concurrent medical conditions. Other factors to consider in considering drug as the cause of the AE:

- Single occurrence of an uncommon event known to be strongly associated with drug exposure (e.g., angioedema, hepatic injury, Stevens-Johnson Syndrome)
- One or more occurrences of an event not commonly associated with drug exposure, but otherwise uncommon in the population (e.g., tendon rupture); often more than once occurrence from one or multiple studies would be needed before the sponsor could determine that there is reasonable possibility that the drug caused the event.
- An aggregate analysis of specific events observed in a clinical trial that indicates the events occur more frequently in the drug treatment group than in a concurrent or historical control group

9.1.3 Unexpected AE or SAR

An AE or SAR is considered unexpected if the specificity or severity of it is not consistent with the applicable product information (e.g., Investigator's Brochure (IB) for an unapproved investigational product or package insert/summary of product characteristics for an approved product). Unexpected also refers to AEs or SARs that are mentioned in the IB as occurring with a class of drugs or as anticipated from the pharmacological properties of the drug but are not specifically mentioned as occurring with the particular drug under investigation.

9.1.4 Serious AE or SAR

An AE or SAR is considered serious if, in the view of either the investigator or sponsor, it results in any of the following outcomes:

• Death:

- Is life-threatening (places the subject at immediate risk of death from the event as it occurred);
- Requires inpatient hospitalization (>24 hours) or prolongation of existing hospitalization;*
- Results in congenital anomaly/birth defect;
- Results in a persistent or significant incapacity or substantial disruption of the ability to conduct normal life functions;
- Important medical events that may not result in death, be life-threatening, or require hospitalization may be considered a serious adverse drug experience when, based upon appropriate medical judgment, they may jeopardize the subject and may require medical or surgical intervention to prevent one of the outcomes listed in the definition. For reporting purposes, also consider the occurrences of pregnancy as an event which must be reported as an important medical event.
- *Note*: In addition to the above criteria, adverse events meeting either of the below criteria, although not serious per ICH definition, are reportable to the Merck in the same timeframe as SAEs to meet certain local requirements. Therefore, these events are considered serious by Merck for collection purposes.
- Is a new cancer (that is not a condition of the study);
- Is associated with an overdose.

*Hospitalization for anticipated or protocol specified procedures such as administration of chemotherapy, central line insertion, metastasis interventional therapy, resection of primary tumor, or elective surgery, will not be considered serious adverse events.

Pregnancy that occurs during the study must also be reported as an SAE.

9.2 SAEs or Serious SARs

9.2.1 Timing

After informed consent but prior to initiation of study medications, only SAEs caused by a protocol-mandated intervention will be collected (e.g. SAEs related to invasive procedures such as biopsies, medication washout).

For any other experience or condition that meets the definition of an SAE or a serious SAR, recording of the event must begin from day 1 of study treatment and continue through the 30-day follow-up period after treatment is discontinued. Serious adverse events (SAEs) caused by a protocol-mandated intervention, or any grade of events of clinical interest (see section 9.4.2.2) that occur within 90 days of the last pembrolizumab administration must be recorded.

9.2.2 Documentation and Notification

SAEs or Serious SARs must be recorded in the SAE console within OnCore® for that subject within 24 hours of learning of its occurrence. Additionally, the

Multicenter Project Manager must also be notified via email of all SAEs within 24 hours of learning of its occurrence.

9.3 Documentation of Non-Serious AEs or SARs

For non-serious AEs or SARs, documentation must begin from day 1 of study treatment and continue through the 30-day follow-up period after treatment is discontinued.

Collected information should be recorded in electronic case report forms (eCRF) for that subject. Please include a description of the event, its severity or toxicity grade, onset and resolved dates (if applicable), and the relationship to the study drug. Documentation should occur at least monthly.

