3.2 Secondary Endpoints

- **3.2.1** Pre- and post-treatment TCR repertoire and neoantigen changes will be defined by changes in TCR clonality and neoantigen load.
- 3.2.2 Pre- and post-treatment changes in STAT and NF-κB expression will be evaluated using mRNAseq analysis and changes in histone acetylation (H3K9Ac and H3K27Ac) levels in a subset of subjects with pre- and post-treatment tumor tissue available (diagnostic TURBT and maximal TURBT or cystectomy tissue available)
- 3.2.3 Toxicity will be evaluated according to guidelines from National Cancer Institute

 Common Terminology for Adverse Events (NCI-CTCAE) criteria version 5.0
 and include all adverse events continuing or occurring 30 days after completion of treatment
- **3.2.4** A pathologic response will be defined as <pT2 (pT0-T1N0M0) and pathologic complete response will be defined as pT0N0M0 at the time of cystectomy at the completion of study treatment.
- 3.2.5 The clinical complete response rate (cT0) is defined as cT0 at the time of maximal TURBT
- **3.2.6** EFS is defined as day 1 of neoadjuvant/protocol treatment to date of first documentation of disease progression (or until recurrence after surgery or radiation) or death due to any cause. Recurrence includes the development of second primary muscle-invasive urothelial malignancies.
- **3.2.7** Overall survival is defined as day 1 of neoadjuvant/protocol treatment to date of death due to any cause. Patients will be censored at date of last follow-up.

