5.2 Treatment Dosage and Administration

After screening and enrollment, blood and archived diagnostic TURBT tumor tissue will be collected from each subject for baseline analyses. Subjects will then be administered pembrolizumab 200 mg IV alone on day 1 and day 22 (Arm 1) or entinostat 5 mg PO followed by pembrolizumab 200 mg IV on day 1, entinostat 5 mg PO on days 8 and 15, and pembrolizumab 200 mg IV on day 22 (Arm 2). Blood and tumor will then be collected from each subject at the time of post-treatment surgery (cystectomy or maximal TURBT).

Agent	Precautions	Dose	Route	Schedule ³
Pembrolizumab ²	Risk for immune-mediated and infusion-related ¹ reactions	200 mg	IV; administer over 30 min (range -5, +10 min)	Administer on Day 1 and Day 22

Entinostat ²	Take on an empty stomach i.e., at least 2 hours after a meal and at least 1 hour before the next meal.	5 mg	Oral (PO)	Administer on Days 1, 8 and 15
-------------------------	--	------	-----------	--------------------------------------

- 1. See Section 5.7.1 for management guidelines for infusion-related AEs
- 2. Entinostat should be taken before the pembrolizumab infusion.
- 3. Allowed window for administration of both pembrolizumab and entinostat is ± 1 day

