Grade ≥ 3 neutropenia, Grade ≥ 3 uncomplicated thrombocytopenia, or Grade 2 complicated thrombocytopenia	Administer symptomatic remedies/start prophylaxis. Hold dose until recovery to Grade 1 or study baseline. If not recovered by next scheduled dose, skip the dose. If recovered by next scheduled dose, resume study drug at prior dose.						

Entinostat may also be held for grade 2 treatment-related adverse events if deemed necessary by the site investigator. If treatment is held due to an adverse event clearly attributable to entinostat that is not listed in the table above and not immune-related, then the pembrolizumab may be continued (i.e. monotherapy). If the event is clearly attributable to pembrolizumab, then both agents will be held. If it is not possible to determine attribution, then both agents will be held. If more than one dose hold for the same event occurs, then the attributable drug should be permanently discontinued (ie, if entinostat is held twice for the same treatment-related adverse event, it will be permanently discontinued, but pembrolizumab may be continued). Doses of either drug should not be delayed, and any held doses will not be made up.

All protocol treatment will be permanently discontinued for any grade 4 non-hematologic event. Permanent discontinuation of all protocol related treatment will also occur for grade 3 non-hematologic adverse events such as myocardial infarction, poorly controlled arrhythmias, and adverse events requiring significant surgical intervention for management. Additionally, if grade >2 drug-related toxicity occurs that does not respond to supportive care within 48 hours and does not resolve to grade ≤ 1 within this timeframe, then the subject will be withdrawn from all protocol treatment and followed until symptom resolution.

Additionally, all protocol treatment will be permanently discontinued if patients have clinical disease progression or development of metastatic disease or require treatment with high dose steroids beyond 2 weeks.

Dose modifications/dose adjustments of either pembrolizumab or entinostat are not allowed.

Safety stopping rules for drug-related toxicity will dictate whether the trial should be halted if 2 subjects have their cystectomy (or maximal TURBT) delayed beyond the 10 weeks from the time of initiation of study therapy due to drug toxicity.

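### Non-serious adverse event recording stops 30 days after the last dose (Day 52), up to 19 days before the latest planned surgery, and conflicts with 7.1.5 and the Time and Events Table.

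*Combined protocol and SAP*

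**What the plan says.** Four places set a 30-day limit. For non-serious events, 9.3 states that "documentation must begin from day 1 of study treatment and continue through the 30-day follow-up period after treatment is discontinued". Section 9.1.1 says: "All AEs from the time of treatment through 30 days following cessation of study therapy must be reported by the investigator". Section 9.4.2.2 repeats that limit for reports to the pembrolizumab supplier. Endpoint 3.2.3 serves objective 2.2.3 (safety, tolerability and feasibility of treatment before surgery or trimodality therapy), and its toxicity evaluation is to "include all adverse events continuing or occurring 30 days after completion of treatment".

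Other places run longer or set no limit:

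- 7.1.5: "Information regarding occurrence of adverse events will be captured throughout the study".
- 8.2 allows surgery (cystectomy or maximal transurethral resection, TURBT) up to 10 weeks after study therapy starts.
- The Time and Events Table marks a toxicity assessment at the pre-surgery and post-surgery visits. Footnote 12 requires the pre-surgery one for cystectomy subjects only. On the post-surgery visit, 8.2.1 says: "This visit should be scheduled 4-8 weeks after cystectomy, or 2-4 weeks after maximal TURBT for trimodality subjects".
- 9.2.1, 8.2.1 and footnote 13 record serious adverse events (SAEs) caused by or related to protocol treatment, and events of clinical interest (ECIs) of any grade, for 90 days from pembrolizumab.

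The halting rule in 5.4 concerns 2 subjects whose surgery is "delayed beyond the 10 weeks from the time of initiation of study therapy due to drug toxicity". Section 10.3 restates it for treatment-related AEs and adds termination at 4 or more subjects.

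**The concern.** Objective 2.2.3 asks whether treatment given before surgery is safe and feasible. The natural period for that question runs at least to surgery, yet the endpoint and the recording rules can close before it. Section 5.4 itself warns that immune-related events can first appear months after dosing ends, so late onset is a foreseeable pattern.

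The sections also give sites different instructions. One that follows 9.3 may leave out a new non-serious finding that one following 7.1.5 would enter. In a multicenter study of 20 subjects, a few events handled differently would visibly change a frequency table of worst grades. The toxicity assessment at the post-surgery visit then has an unclear purpose, because new non-serious findings with onset after the limit have no required place in the data or the endpoint.

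**Working it through.** **Inputs**

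- Last planned dose: pembrolizumab, both arms, "Administer on Day 1 and Day 22", with a window of ±1 day (5.2). It cannot move much later: "Doses of either drug should not be delayed, and any held doses will not be made up" (5.4). It can be earlier if doses are held or treatment stops.
- Recording limit: 30 days after treatment ends (3.2.3, 9.1.1, 9.3, 9.4.2.2), counted here from the last dose.
- Surgery limit: 10 weeks from initiation (8.2), with initiation on Day 1.
- Post-surgery visit: 28 to 56 days after cystectomy, 14 to 28 days after TURBT (8.2.1).

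The plan states no figure of its own for this interval, so there is none to reproduce.

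**Length of the gap.** Recording ends on last dose + 30. The surgery limit is Day 1 + 70 = Day 71.

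| Last dose | Recording ends | Maximum gap |
|---|---|---|
| Day 22 | 22 + 30 = Day 52 | 71 − 52 = 19 days |
| Day 15 (Arm 2, no Day 22 dose) | 15 + 30 = Day 45 | 71 − 45 = 26 days |
| Day 1 only | 1 + 30 = Day 31 | 71 − 31 = 40 days |

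The ±1 day window moves the first row to 18–20 days. Counting Day 1 as the first of the 70 days puts the limit at Day 70 and the gap at 18 days.

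These are maxima for surgery inside the 10-week limit. After a Day 22 last dose and surgery on Day S, the gap is S − 52 when S is above 52, and zero otherwise. The documents do not give the expected distribution of S.

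**What is required for an onset on Day 53–71 (last dose Day 22)**

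- Treatment-related SAE or ECI: recorded to 22 + 90 = Day 112, which is 41 days past the surgery limit. If only the Day 1 pembrolizumab dose was given, 1 + 90 = Day 91 is still 20 days past it.
- Event with onset by Day 52 that continues: followed until it resolves or stabilizes (9.4.2.4), and 3.2.3 counts continuing events.
- New non-serious event that is not an ECI: not required by 9.1.1, 9.3 or 9.4.2.2, outside 3.2.3, but captured under 7.1.5. This is the gap.

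ECIs do not fill it. Section 9.4.2.7 lists only pembrolizumab overdose and a combined liver enzyme and bilirubin pattern.

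**When toxicity is next assessed.** With surgery on Day 71, the post-surgery visit falls on 71 + 28 = Day 99 to 71 + 56 = Day 127 for cystectomy, or 71 + 14 = Day 85 to 71 + 28 = Day 99 for TURBT. Even the earliest permitted visit is after Day 52 for cystectomy from Day 25 (25 + 28 = 53) or TURBT from Day 39 (39 + 14 = 53). A late visit can still collect an earlier onset, so this shows the mismatch without proving that data are lost. Because of footnote 12, a TURBT subject needs no toxicity assessment between Day 22 and the post-surgery visit, an interval of 63 to 77 days when surgery is on Day 71 (85 − 22 and 99 − 22).

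**The case against.** The best defense is that the events that matter are already covered. Treatment-related SAEs run to 90 days. Seriousness includes hospitalization, its prolongation and important medical events, so much significant perioperative toxicity would qualify. Section 9.1.1 also asks for drug-related SAEs at any time. Toxicity that begins by Day 52 is followed through. Section 9.3 sets a minimum and does not forbid later entries. The 30 days look deliberate: the summary of changes for the amendment that added trimodality therapy records a move of endpoint 3.2.3 from 90 to 30 days. Finally, collecting non-serious events up to 8 weeks after cystectomy brings in surgical morbidity that says little about the drugs.

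All of this stands as a limit on the size of the problem. It does not reconcile 9.3 with 7.1.5, and it does not bring a late non-serious event before surgery into the endpoint.

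Three stronger readings are tempting, and the documents do not support them:

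- **The halting rule would miss cases.** Sections 5.4 and 10.3 count surgeries delayed by treatment toxicity. Neither requires onset within 30 days or an entry in the AE table. A delayed surgery among 20 subjects is visible, and its cause has to be judged anyway.
- **A steroid taper of at least 4 weeks would carry a late event past week 10.** No section says that surgery must wait for a taper to finish.
- **Chemoradiation toxicity would enter the table unlabelled.** Onset date and relationship to study drug are recorded for each AE (7.1.5, 9.3), so events can be separated. The overlap is also narrow: the post-surgery visit should precede chemoradiation, so a start before Day 52 needs TURBT by about Day 37 (37 + 14 = 51).

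**Conclusion.** The concern holds as an internal inconsistency with a bounded gap in the safety endpoint. Under the 30-day sections, a new non-serious, non-ECI event that starts after recording closes and before surgery need not be recorded and is not part of 3.2.3. The exposure is at most 19 days per subject after a full course, or 26 or 40 days when treatment ends on Day 15 or Day 1. It is nil for a subject treated through Day 22 with surgery by Day 52.

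A reader might infer that all toxicity after Day 52 goes unrecorded, or that no perioperative non-serious events would be tabulated. Neither follows: serious treatment-related events are covered past week 10, and early surgery leaves some postoperative days inside the window. The gain for the halting rule is only documentary, since AE records that reach surgery would support the stated cause of any delay.

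This rests on reading treatment end as the last dose, initiation as Day 1, and 3.2.3 as events up to 30 days. How many subjects are affected depends on surgery dates that the documents do not give. The primary gene-signature analysis is untouched. The correction is inexpensive and should be made.

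**What to change.** Reconcile 3.2.3, 7.1.5, 9.1.1, 9.3 and 9.4.2.2 on one rule: record all AEs to the later of 30 days after the last dose or the post-surgery visit already in the schedule. At minimum, recording should reach surgery.

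In 10.3, tabulate events separately by onset date as before surgery, after surgery, and after the start of chemoradiation. Keep the 30-day table alongside, so that the present definition can still be reported.

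Reconcile footnote 12 with the rule, for example by collecting TURBT subjects' events with onset dates at the post-surgery visit.

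The cost is wording in these sections and some extra AE entries, with no added visit. The downside is more post-surgical events to attribute. Tabulating by onset period keeps those apart from events before surgery.

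If the sponsor prefers to keep 30 days, 7.1.5 should say so. The plan should then state what the post-surgery toxicity assessment is for, and that the endpoint may stop before surgery.
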